2.2 Secondary Efficacy

- 2.21 To compare the surgical complication rates between oral SBI vs. placebo up to 1 month post-surgery (safety endpoint).
- 2.22 To compare the QOL, as derived from the previously-validated Symptom Distress Scale, the PQL (Postoperative Quality of Life questionnaire), and the uniscale (overall QOL item) between patients receiving oral SBI vs. placebo.
- 2.23 To compare the grade 2 or worse adverse event rates for patients receiving oral SBI vs. placebo.
- 2.24 To characterize the adverse event profile of oral SBI in postoperative gynecological cancer patients (safety endpoint).
- 2.25 To compare supplement adherence between patients receiving oral SBI vs. placebo.

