In addition to submitting initial IRB approval documents, ongoing IRB approval documentation must be on file (no less than annually) at the Registration Office ([contact]). If the necessary documentation is not submitted in advance of attempting patient registration, the registration will not be accepted and the patient may not be enrolled in the protocol until the situation is resolved.

When the study has been permanently closed to patient enrollment, submission of annual IRB approvals to the Registration Office is no longer necessary.

6.14 Prior to accepting the registration, the registration/randomization application will verify the following:

- IRB approval at the registering institution
- Patient eligibility
- Existence of a signed consent form
- Existence of a signed authorization for use and disclosure of protected health information

6.15 Intervention on this protocol must commence at Mayo Clinic Rochester, under the supervision of a medical oncologist.

6.16 Intervention cannot begin prior to registration and must begin \leq 7 days after registration.

6.17 Pre-intervention tests/procedures (see Section 4.0) must be completed within the guidelines specified on the test schedule.

6.18 All required baseline symptoms (see Section 10.6) must be documented and graded.

6.19a Study agent is available on site

6.19b Blood draw kit is available on site.

6.19c Patient questionnaire booklet is available on site; copies are not acceptable for this submission.

6.19d At the time of randomization, the following will be verified:

- Patient has/not given permission for his/her blood sample(s) to be stored and used in future research of ovarian cancer at Mayo Clinic.
- Patient has/not given permission for his/her blood sample(s) to be stored and used in future research at Mayo Clinic to learn about, prevent, or treat any other health problems
- Patient has/not given Mayo Clinic permission to give his/her blood sample(s) to outside institutions

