10.6 Required Routine Reporting

Adverse events to be graded at each evaluation and preintervention symptoms/conditions to be evaluated at baseline per the CTCAE v4.0 grading unless otherwise stated in the table below:

System Organ Class (SOC)	Adverse event/Symptoms	Baseline	Each evaluation
Gastrointestinal disorders	Abdominal pain	X	X
	Bloating	X	X
	Diarrhea		X
	Baseline number of stools per day	X	
	Flatulence	X	X
	Nausea	X	X
	Vomiting	X	X
General disorders and administration site conditions	Fatigue	X	X
Infections and infestations	Wound infection	X	X
Injury, poisoning and procedural complication	Wound complication	X	X
	Wound dehiscence	X	X

10.61 Submit via appropriate MCCC Case Report Forms (i.e., paper or electronic, as applicable) the following AEs experienced by a patient and not specified in Section 10.6

10.611 Grade 2 AEs deemed *possibly, probably, or definitely* related to the study intervention or procedure.

10.612 Grade 3 and 4 AEs regardless of attribution to the study intervention or procedure.

10.613 Grade 5 AEs (Deaths)

10.6131 Any death within 30 days of the patient's last study treatment or procedure regardless of attribution to the study intervention or procedure.

10.6132 Any death more than 30 days after the patient's last study intervention or procedure that is felt to be at least possibly intervention related must also be submitted as a Grade 5 AE, with a CTCAE type and attribution assigned.

11.0 Intervention Evaluation: None**12.0 Descriptive Factors: None****13.0 Follow-up Decision at Evaluation of Participants**

- 13.1 Participants will receive 3 cycles of therapy (12 weeks) with oral SBI or placebo, followed by a 4 week observation visit. No additional follow-up is required for these patients beyond the 4 week observation time point.
- 13.2 Participants who go off the intervention early for unacceptable adverse events or patient refusal of further treatment will go to the observation phase. Patients can continue in the observation phase for total of 16 weeks of study participation.
- 13.3 Participants where post-operative problems occur, study treatment cannot begin, and participant agrees to complete questionnaires will crossover to QOL assessment only. These participants will be followed per the test schedule (Section 4.0).

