We expect about 10% of patients to experience grade 3 or worse adverse events (at least possibly related to the study intervention). In addition, we expect less than 1% of patients to experience a Grade 5 adverse event, at least possibly related to the study intervention. Accrual will be temporarily suspended to this study if at any time we observe adverse events that satisfy any of the following within each arm separately (i.e. if any of the following occur in arm A or arm B, we will suspend accrual to the trial):

- If at any time 4 or more in the first 20 treated patients (or 20% or more after the first 20) experience a Grade 3 or worse adverse event (possibly, probably, or definitely related to the intervention).
- If at any time, 1 patient experiences a grade 5 adverse event (possibly, probably, or definitely related to the intervention).

We note that we will review all Grade 5 adverse events on a case-by-case basis as well (regardless of attribution), and may suspend accrual after just one Grade 5 event, if we feel it is necessary for patient safety.

16.6 Definitions and Analyses of Secondary Endpoints: All these endpoints will be assessed individually and will also be compared between the 2 arms. Monthly phone calls may be used to collect the secondary endpoint information for each patient, including adverse events, surgical complications, and other data (e.g. patient reported weight, intervention compliance, etc.). We will be assessing, reporting on, and potentially analyzing all the data collected from these monthly telephone calls.

16.61 Adverse Events: All eligible patients who have initiated therapy will be considered evaluable for adverse event analyses. The maximum grade for each type of adverse event will be recorded for each patient up to 16 weeks post-randomization (12 weeks of intervention + 1 month post-intervention observation timepoint), and frequency tables will be reviewed to determine adverse event

patterns. The overall adverse event rates for grade 2 or higher adverse events, will be compared using Chi-Square or Fisher's Exact tests. In addition, the surgical complication rates (up to 1 month post-surgery) will also be compared between the 2 arms using Chi-Square or Fisher's Exact tests.

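### The grade 2+ adverse event comparison in 16.61 makes no use of the baseline grades the protocol requires, so persisting postoperative symptoms count as events and dilute the contrast between arms

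*Combined protocol and SAP*

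**What the plan says.** Objective 2.23 reads: "To compare the grade 2 or worse adverse event rates for patients receiving oral SBI vs. placebo". Section 16.61 carries it out in three steps.

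- Analysis set: "All eligible patients who have initiated therapy will be considered evaluable for adverse event analyses".
- Summary per patient: "The maximum grade for each type of adverse event will be recorded for each patient up to 16 weeks post-randomization".
- Test: "The overall adverse event rates for grade 2 or higher adverse events, will be compared using Chi-Square or Fisher's Exact tests".

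Neither 2.23 nor 16.61 mentions baseline grade, new onset, worsening or attribution.

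Baseline grades are nevertheless required. Section 6.18 states: "All required baseline symptoms (see Section 10.6) must be documented and graded". Section 10.6 calls for "preintervention symptoms/conditions to be evaluated at baseline per the CTCAE v4.0 grading" and marks nine graded terms at baseline: abdominal pain, bloating, flatulence, nausea, vomiting, fatigue and three wound terms. Diarrhea is graded only after baseline; a baseline stool count stands in for it. Section 18.11 includes a Baseline Adverse Event Form.

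For events outside the 10.6 list, 10.611 asks for grade 2 only when at least possibly related, while 10.612 asks for grades 3 and 4 whatever the attribution.

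**The concern.** Section 3.14 admits patients within 7 days of surgery that went beyond a simple hysterectomy. The solicited terms are largely what such patients can be expected to have on entry. They also overlap with effects that 15.16 reports for the product, such as stomach cramps, nausea and fatigue. A symptom graded 2 at entry and still graded 2 at a later assessment is counted exactly like one that began on study product. A patient so counted cannot be counted again, so a real new event in that patient adds nothing to the comparison.

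The other outcomes measured at baseline are analyzed as changes: the primary endpoint (16.11), the QOL scores (16.63) and the biomarkers (16.64). The adverse event comparison is the exception. Section 7.1 also allows the first dose up to 7 days after registration, so pre-dose days can fall inside the post-randomization window.

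The collection rule raises a second problem. Constipation, headache and neuropathy appear in 15.16 or 15.19 as reported or possible effects but are not on the 10.6 list. At grade 2 they enter only if someone attributes them to the intervention or procedure. The pooled rate therefore mixes solicited events of any attribution, related unsolicited grade 2 events, and grade 3+ events.

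At stake is sensitivity. This is one of the results that 16.11 says will inform the final decision, and dilution could hide harm or benefit.

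**Working it through.** **The plan's own figure.** The documents give no rate, power or alpha for the grade 2+ comparison. The only design calculation is for the primary endpoint, and it reproduces: 4 × (1.960 + 0.842)² / (ln 2)² rounds up to 66 events. It does not bear on this point.

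**Inputs from the documents.** 35 evaluable patients per arm (16.11), with at most 50 per arm (16.2). The number who start therapy, which is the adverse event set, may differ from 35. Two-sided alpha of 0.05 is borrowed from the primary test.

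**Assumptions.** New-onset grade 2+ rates p of 20% and 45%. A share b of each arm has an entry symptom recorded again at grade 2+ after randomization. The share b is equal in the two arms and independent of new onset.

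**Formulas.** Observed rate = b + (1−b)p, so the observed difference is (1−b) × 25 points. With observed rates c and t and mean rate m:

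- se0 = √(2m(1−m)/n)
- se1 = √((c(1−c) + t(1−t))/n)
- power = Φ((t − c − 1.96·se0)/se1)

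**Two rows in full, n = 35.**

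- b = 0: c = 0.20, t = 0.45, m = 0.325, se0 = 0.1120, se1 = 0.1079. (0.25 − 0.2194)/0.1079 = 0.283, so power is 61%.
- b = 0.3: c = 0.3 + 0.7 × 0.20 = 0.44, t = 0.3 + 0.7 × 0.45 = 0.615, se0 = 0.1193, se1 = 0.1175. (0.175 − 0.2339)/0.1175 = −0.501, so power is 31%.

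| b | Observed rates | Difference (points) | Power, 35 per arm | Fisher exact, 35 per arm | Power, 50 per arm |
|---|---|---|---|---|---|
| 0 | 20% vs 45% | 25 | 61% | 53% | 77% |
| 0.1 | 28% vs 50.5% | 22.5 | 49% | 40% | 64% |
| 0.2 | 36% vs 56% | 20 | 39% | 29% | 52% |
| 0.3 | 44% vs 61.5% | 17.5 | 31% | 22% | 42% |
| 0.5 | 60% vs 72.5% | 12.5 | 19% | 14% | 26% |
| 0.7 | 76% vs 83.5% | 7.5 | 12% | 7% | 15% |

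**Prevalence is not carry-over.** b is prevalence at entry multiplied by persistence at grade 2+. If half of entry symptoms persist, prevalences of 30%, 50% and 70% give b = 0.15, 0.25 and 0.35, and power of 43%, 35% and 27%. If a fifth persist, b = 0.06, 0.10 and 0.14, and power is 53%, 49% and 44%.

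**Other rates.** With 20% vs 50% at 35 per arm, power is 76% at b = 0, 52% at b = 0.2 and 27% at b = 0.5. The pattern is the same.

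**Type I error.** With a 20% new-onset rate in both arms and 35 per arm, the exact size of Fisher's test lies between 2.5% and 2.9% for the values of b in the table. Carry-over does not inflate it.

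The mixing of attribution rules follows from the text of 10.6, 10.611 and 10.612. The documents give nothing from which to size it.

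**The case against.** **A baseline symptom does not count automatically.** The window in 16.61 is post-randomization, and the first scheduled assessment after baseline is Day 1 of Cycle 2 (Section 4.0), with 28-day cycles. Symptoms that settle before then may never be recorded, since the documents do not say whether each visit looks back over the whole interval. This stands. A reader might infer that everything present before dosing becomes an event; the text does not support that.

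**Persistence may be the effect of interest.** The trial tests whether SBI speeds recovery, and 2.23 sits under secondary efficacy without the safety label that 2.21 and 2.24 carry. If nausea resolves on SBI and persists on placebo, the maximum-grade rule captures some of that, while a new-or-worsened rule discards it. This stands, and it is why the existing comparison should not be replaced. It also means that equal b in both arms is a simplification.

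**Baseline grades are incomplete.** Diarrhea has none, and unsolicited terms have none required. Section 4.0 allows the baseline assessment up to 21 days before randomization, while surgery falls within 7 days before registration, so a recorded grade could precede surgery. This stands and shapes the fix.

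**The stakes are limited.** This is an unpowered secondary comparison in a randomized, double-blind pilot. Stopping rules, frequency tables by event type and board review do not depend on it. That is true and limits the weight of the point. It does not explain why grades that must be collected are left unused.

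**Conclusion.** The point holds as a loss of sensitivity. Section 16.61 fixes a concrete rule, and that rule lets persisting surgical symptoms count as events. The expected difference shrinks by (1−b). Under the assumed 20% vs 45% with 35 per arm, the loss is 12 points of power at b = 0.1 (61% to 49%), 22 at b = 0.2, 30 at b = 0.3 and 42 at b = 0.5. The new-onset rates, b and its equality across arms are all assumptions.

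A reader might go further and infer that carry-over swamps any SBI effect. The documents give no grade 2+ rate at baseline or afterwards, so the loss could be modest or severe. Nor do they support reading the dilution as bias toward one arm or as a raised false-positive rate.

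The mismatch with objective 2.23 needs no assumption: under 10.611 the pooled rate omits unrelated grade 2 events outside the solicited list. Its size is unknown.

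**What to change.** Amend 16.61 as follows.

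1. Add a comparison of new or worsened grade 2+ events on the terms solicited in 10.6. The reference is the last postoperative, pre-dose grade for the same term, named as such so that a preoperative grade does not serve. State how patients without such a grade are handled, and report their number.
2. For diarrhea, take the baseline stool count as the reference. Treat unsolicited terms as absent at baseline unless one was recorded.
3. Keep the maximum-grade comparison alongside, because persistence of symptoms may itself respond to SBI.
4. Report separately solicited grade 2+ (any attribution), any grade 3+, and related grade 2+. Label them descriptive secondary comparisons.

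For patients with a postoperative baseline grade, the cost is wording and a little programming. The new table will show lower rates than the maximum-grade table, since a patient at grade 2 on entry must reach a higher grade on that term to count. There will also be several secondary tests without multiplicity adjustment instead of one, which is why they should be read descriptively.

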4.0 Test Schedule

Tests and procedures	Active Monitoring Phase				Observation/crossover (ends after 16 weeks of total study participation)
	≤21 days prior to randomization	Day 1 of Cycle 2 and 3 (+/- 3 days)	Weekly from registration for 12 weeks total	At the end of intervention (+/- 3 days)	
Patient assessment (includes weight**)	X				
Adverse event assessment	X	X**		X**	X**
Pregnancy test ¹ (Serum)	X				
Hematology group					
HgB					
WBC	X				
PLT					
ANC					
Chemistry group					
Creatinine	X				
Patient Questionnaire					
Booklets ² , (Appendix 2-5)	X		X	X	X
Blood specimens (see Section 14.0) ^{3,R}	X	X*			

1. For women of childbearing potential only. Must be done ≤7 days prior to registration.
2. Patient questionnaire booklets **must** be used; copies are not acceptable for this submission. Patients are required to fill out the questionnaires at baseline, and weekly for the duration of study participation, (16 weeks total, includes patients who never started therapy).
3. Blood specimens will be collected and submitted at baseline. Kits are required. Baseline blood specimen is to be collected after consent and prior to patient receiving study agent.

R Research funded (see Section 19.0)

*These blood draws are optional but strongly recommended.

** If patient cannot return, this assessment can be done by phone by the study coordinator (includes patient reported weight). However, study questionnaires must be mailed back.

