8.0 Dosage Modification Based on Adverse Events

There are no dose modifications in this trial. If the patient experiences a grade 1 or worse adverse event that is thought to be related to the study intervention, the patient should discontinue the intervention and proceed to the 4 week post intervention observation.

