18.12 Test Schedule Material(s)

CRF	Active-Monitoring Phase (Compliance with Test Schedule Section 4.0)		
	At each evaluation during the intervention period	At end of intervention	Observation/Crossover
Nurse/CRA Evaluation/Intervention Form	X	X	
Nurse/CRA Observation Form (4 weeks after completion of intervention)			X
Adverse Event Form	X	X	X*
Research Blood Submission Form	X (see Section 14.0)		
Patient Questionnaire	X ¹	X ¹	X
Patient Questionnaire Booklet Compliance Form	X ²	X ²	
End of Active Intervention/Cancel Notification Form		X	
Notification Form – Grade 4 or 5 Non- AER Reportable Events/Hospitalization Form	At each occurrence (see Section 10.0)		
ADR/AER	At each occurrence (see Section 10.0)		

* If the patient does not start therapy, adverse events will not be collected.

1. Patient questionnaire booklet **must** be used; copies are not acceptable for this submission.

2. This form must be completed **only** if the Patient Questionnaire contains absolutely **NO** patient provided assessment information.

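### The 16-week grade 2+ adverse event comparison depends on follow-up after an early stop, which the documents set at 4 weeks in some places and at week 16 in others

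*Combined protocol and SAP*

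**What the plan says.** Section 16.61 sets the population: "All eligible patients who have initiated therapy will be considered evaluable for adverse event analyses". It sets the window: "The maximum grade for each type of adverse event will be recorded for each patient up to 16 weeks post-randomization". It sets the test: "The overall adverse event rates for grade 2 or higher adverse events, will be compared using Chi-Square or Fisher's Exact tests". It has no rule for a treated patient who is observed for less than 16 weeks. The comparison is a named secondary goal (2.23).

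Four places bear on how long a patient is followed after stopping product early:

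- **8.0.** The trigger reads "If the patient experiences a grade 1 or worse adverse event that is thought to be related to the study intervention", and then "the patient should discontinue the intervention and proceed to the 4 week post intervention observation".
- **18.12.** One row is headed "Nurse/CRA Observation Form (4 weeks after completion of intervention". The Adverse Event Form is a separate row. It is also marked for observation/crossover but carries no time limit.
- **13.2.** For patients who stop because of unacceptable adverse events or refusal: "Patients can continue in the observation phase for total of 16 weeks of study participation".
- **4.0.** The last column, in which adverse event assessment is marked, is headed "Observation/crossover (ends after 16 weeks of total study participation". A footnote allows assessment by phone.

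Section 16.6 adds that monthly phone calls may be used to collect adverse events; it does not require them.

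**The concern.** A crude proportion over a fixed window is a fair comparison only if both arms are watched for the whole window, or fall short of it equally. Here the trigger for stopping is a product-related event, even a mild one, so the number of early stops may differ by arm. If adverse event collection ends 4 weeks after a stop, the arm with more stops is watched for less time, and 16.61 still counts its patients as if they had been seen to week 16.

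The patients affected are those who stop without having had a grade 2+ event, for example after a related grade 1 event or by refusal. Their later grade 2+ events would go unrecorded. Such events are plausible. Section 16.11 says patients often begin chemotherapy 6 weeks after surgery, and the solicited events in 10.6 include nausea, vomiting, diarrhea and fatigue. A patient who stops at week 2 would leave 4-week follow-up at about the time chemotherapy begins.

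At stake is the safety estimate that this pilot passes to the larger study it is meant to prepare.

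**Working it through.** **No plan figure to reproduce.** The documents give no expected grade 2+ rate, no early-stop rate and no power for this comparison. The 10% in 16.52 concerns related grade 3 or worse events. All rates below are assumptions.

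**The passages side by side, for a stop at week 2**

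| Place | Follow-up after the stop | Ends at about |
|---|---|---|
| 8.0 | 4-week observation | week 6 |
| 18.12, observation form | 4 weeks after completion | week 6 |
| 13.2 | may continue to 16 weeks in total | up to week 16 |
| 4.0, observation column | to 16 weeks in total | week 16 |

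A patient who completes product has four post-baseline adverse event evaluations under 4.0: Day 1 of Cycles 2 and 3, end of intervention, and observation. On the 4-week reading, a week-2 stopper has two, and the last falls 6/16 = 38% of the way through the window.

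**Model.** Background 16-week grade 2+ risk R = 50% in both arms, constant hazard. Shares stopping at week 2: 30% on SBI and 10% on placebo. Let g be the share of stops caused by a grade 2+ event; those patients count as events however long they are followed.

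- Risk seen by week 6: F = 1 - 0.5^(6/16) = 0.229.
- Recorded arm rate: (1 - p)R + p[g + (1 - g)F], where p is the share stopping.
- Rate with full follow-up: the same, with R in place of F.
- Distortion of the difference: -(0.30 - 0.10)(1 - g)(0.500 - 0.229) = -5.4(1 - g) points.

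For g = 0, the recorded SBI rate is 0.7 x 0.5 + 0.3 x 0.229 = 41.9%, and the placebo rate is 0.9 x 0.5 + 0.1 x 0.229 = 47.3%.

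| g | Full follow-up, SBI vs placebo | True difference | Recorded, SBI vs placebo | Recorded difference |
|---|---|---|---|---|
| 0% | 50.0% vs 50.0% | 0 | 41.9% vs 47.3% | -5.4 |
| 25% | 53.8% vs 51.3% | +2.5 | 47.7% vs 49.2% | -1.6 |
| 50% | 57.5% vs 52.5% | +5.0 | 53.4% vs 51.1% | +2.3 |
| 100% | 65.0% vs 55.0% | +10.0 | 65.0% vs 55.0% | +10.0 |

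(Differences are in points, from unrounded rates.)

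**Where the recorded ranking changes.** The recorded rates are equal when g + (1 - g)F = R, that is g = (0.500 - 0.229)/0.771 = 35%. Below that share the arm with more stops is recorded as better; above it, as worse. Over R = 30% to 70% and stops at week 2, 4 or 8, this break-even share runs from 8.5% to 53%.

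**Sensitivity at g = 0.** Over the same grid, with 30% versus 10% stopping, the false difference is -1.3 to -6.7 points under constant hazard. It is -0.7 to -3.6 points if the hazard is front-loaded (cumulative hazard proportional to the square root of time). Under a normal approximation, the chance of a significant result in that direction is about 3-8% at 35 per arm and 3-10% at 50 per arm, against 2.5% nominal.

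**16-week reading.** With F replaced by R for every stopper, the distortion is zero.

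**The case against.** The strongest reply is that the plan already provides for full follow-up. Section 13.2 is the provision written for early stoppers, and it allows 16 weeks in total. The 4.0 observation column runs to 16 weeks with adverse event assessment marked and phone contact allowed. Section 16.61 itself speaks of 16 weeks for each patient. In 18.12 the 4-week date belongs to the Nurse/CRA form, not to the Adverse Event Form. All of this stands, so a reader who infers that early stoppers certainly have less observed time goes further than the documents do. It does not settle the matter: 13.2 is only permissive, 8.0 names 4 weeks, the calls in 16.6 are optional, and 16.61 is silent on any shortfall.

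A reader might also infer that the arm with more early stops will look safer. The documents do not support that. The trigger in 8.0 includes grade 2 and worse, and a stop for such an event is already counted. As the table shows, when half of stops are of that kind the arm with more stops still looks worse, though by less than it should.

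It is also fair to say that the stopping rates and risks are assumed, that a falsely significant result is unlikely at this sample size, and that this is a secondary comparison in a pilot. The suspension rules in 16.52 do not use this test.

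**Conclusion.** The point holds in conditional form. The documents give two answers on how long adverse events are collected after an early stop, and 16.61 makes a crude 16-week comparison with no rule for shorter observation. If the 4-week reading is followed, the arm with more early stops has its grade 2+ rate understated relative to full follow-up, and a true excess can be shrunk or hidden. With 50% background risk and week-2 stops in 30% versus 10%, the difference is distorted by about 5.4 points when no stop is due to a grade 2+ event, 4.1 points when 25% are, and 2.7 points when 50% are. If the 16-week reading is followed, there is no bias.

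These sizes rest on assumed risks, stop rates and stop times, and on constant hazard; events concentrated early would reduce them. The direction of the recorded difference cannot be predicted from the documents. The 1-month surgical complication rate is largely unaffected, because even an immediate stop followed by 4 weeks covers about that period. This is worth correcting before analysis, but it does not touch the primary endpoint.

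**What to change.** Reconcile 4.0, 8.0, 13.2 and 18.12 on adverse event collection after an early stop. The Adverse Event Form should be completed at the same weeks (4, 8, 12 and 16), by phone if needed, for every patient who started product, whether or not she stopped. This concerns data collection only; the rule for stopping product is not at issue. With follow-up aligned, the 16.61 chi-square or Fisher comparison can stay as it is.

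Add to 16.61 a sensitivity analysis for patients still not observed to week 16: time to first grade 2+ event, or an exposure-adjusted rate, with each patient at risk up to her last adverse event assessment. State that this censoring may be informative, because stopping can itself follow from adverse events. For that reason it should supplement aligned follow-up, not replace it. It needs event onset dates, which may be coarse when events are graded about every four weeks.

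The cost is protocol and SAP wording plus one or two extra phone contacts per early stopper, in a trial that already collects weekly questionnaires to week 16 and allows adverse event assessment by phone.
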